Protocol #: 19-0278

Title: The effect of a gas-filled intragastric balloon or Endoscopic Sleeve Gastroplasty for weight loss compared with a meal replacement weight loss program on gastric emptying, hormonal adaptation to weight loss, and hunger

PI: [name], University of Colorado School of Medicine

Version Date: 2-Nov-21

SPECIFIC AIMS: The disease obesity continues to be a major health issue in the US with over one third of the population having a mass index $>30 \text{ kg/m}^2$. Obesity is associated with serious cardiometabolic complications including diabetes, hypertension, dyslipidemia and myocardial infarction. Rates of successful obesity treatment with weight loss and weight maintenance remain low. Several endoscopic bariatric therapies and procedures have been approved for use in the United States, including three intragastric balloon systems (2 fluid-filled and one gas-filled) and endoscopic sleeve gastroplasty (ESG), both of which have lower risks than bariatric surgery and do not alter gastrointestinal anatomy. Weight loss with all intragastric balloons and ESG is higher than lifestyle therapy or weight loss medications, but less than bariatric surgery. Unlike weight loss medications where weight loss from the medication is regained within 6-8 months after therapy ends, weight loss maintenance with intragastric balloons remains high with 66-88.5% of the weight loss maintained 6 months after device removal. Data suggests that space occupying devices with a volume of 400 ml or more in the stomach increase feelings of fullness and result in weight loss, but this does not explain the prolonged effect of weight loss maintenance after balloon removal. Although few studies have investigated the mechanism of action of fluid-filled balloons and one study with 4 patients undergoing ESG on weight loss, these data suggest that gastric emptying as well as space occupation contribute to weight loss. However, no studies have investigated the mechanisms of action of gas filled intragastric balloons on weight loss.

Understanding the mechanisms responsible for weight loss with the gas filled intragastric balloon system and eSG as well as any weight loss independent effects on blood glucose control would lay the groundwork for studies evaluating predictors of response to improve patient selection as well as studies understanding the mechanisms behind weight loss maintenance and developing strategies to prolong weight loss maintenance. **Therefore, the purpose of this pilot study is to determine the effects 10% total body weight loss (%TBWL) in patients with obesity treated with the intragastric balloon (GF- IGB) system or ESG compared to patients with obesity treated with a meal replacement program (MRP) on 1) gastric emptying, 2) hormonal adaptation to weight loss and 3) hunger. The following specific aims will be evaluated:**

AIM 1. Gastric emptying measured by technetium 99 gastric emptying study. Hypothesis 1. We hypothesize that treatment with GF-IGB and ESG will result in greater gastric retention of contents at 2 hours compared with patients who are treated with MRP.

AIM 2. Acyl-Ghrelin, glucose and insulin will be measured at multiple times points during a mixed meal test (MMT). Hypothesis 2. We hypothesize that weight loss induced increase in active ghrelin concentrations seen during a mixed meal tolerance test will be lower in patients treated with GF-IGB and ESG compared with patients treated with MRP, but there will be no difference in glucose and insulin concentrations.

Aim 3. Level of hunger will be measured using a visual analog scale. Hypothesis 3. We hypothesize that hunger will increase before and during a MMT after weight loss with MRP but will not change from baseline after weight loss with GF-IGB or ESG treatment.

1. Background and Significance

Obesity is a chronic disease which is associated with and contributes to multiple medical co-morbidities including but not limited to cardiovascular disease, diabetes, nonalcoholic fatty liver disease, and many different cancers. Obesity is also associated with an increased risk of all-cause mortality. Despite these known risks, treatment remains limited. This has contributed to the increase in the prevalence of obesity with 42.4% of adults in the US adults having a body mass index (BMI) >30 kg/m² of¹.

Endoscopic bariatric therapies are a new class of treatment for obesity which have demonstrated more weight loss than lifestyle therapy alone and fewer complications than bariatric surgery with less weight loss than bariatric surgery²⁻⁵. Four endoscopic devices are currently approved by the FDA for the treatment of obesity, including two intragastric balloons (IGB). One of the balloons systems are fluid filled (FF-IGB) and one is gas filled (GF-IGB). Although the GF-IGB system is swallowed, all the balloon systems require an endoscopist for endoscopic removal. In clinical registry series, these balloons demonstrate similar weight loss at 6 months⁶⁻⁸. Unlike weight loss medications, weight loss maintenance is prolonged after IGB removal, which was demonstrated meta-analysis of studies and case series outside of the US of the single FF-IGB demonstrated weight loss maintenance after balloon removal⁹ and in the US pivotal trials²⁻⁴. While the occupancy of space in the stomach by IGB is known to induce satiation and satiety^{10, 11}, this mechanism is only present with the IGB in place. Therefore, the prolonged effects of weight loss maintenance after IGB removal suggest other mechanisms contributing to weight loss with IGB treatment beyond space occupation. ESG is completed endoscopically with a device that has FDA 510k clearance for tissue apposition in the GI tract. Weight loss with ESG in a recent meta-analysis in 1772 patients demonstrated 16.5% TBWL at 12 months and 17.2% TBWL at 18-245 months¹². **Understanding the mechanisms contributing to weight loss with the GF-IGB system and ESG will lay the groundwork for future studies to enhance the effect of IGBs and ESG on initial weight loss, patient selection, and weight loss maintenance; increasing benefits to patients treated with IGBs or ESG.**

FF-IGB are known to delay gastric emptying^{10, 11}. This is consistent with practice patterns as patients reliably have food left in their stomachs after an overnight fast requiring multiple days of liquid diet prior to endoscopic removal to avoid aspiration. In one study, the FF-IGB delayed gastric emptying compared to both baseline and a control group and the change in gastric emptying was associated with weight loss (12). Gastric emptying has been studied in only 4 patients before and after ESG. In these 4 patients, there was a 90 minute increase to the time for 50% of emptying of solid foods, however the limited number of patients in that study reduce overall certainty of the effect of ESG on gastric emptying¹³. No studies have investigated the effects of the GF-IGB on gastric emptying. **This protocol will clarify the effects of the GF-IGB and ESG on gastric emptying compared with a control group matched on weight loss. This will elucidate the weight loss independent effects of the devices since patients will be studied at baseline and 10% total body weight loss.**

Another possible mechanism by which IGBs and ESG may induce weight loss and weight loss maintenance is through alterations in gut hormones. Ghrelin is a hormone secreted by X/A like cells, which are predominantly in the fundus of the stomach¹⁴. Ghrelin concentrations fluctuate with eating, increasing pre-meals and decreasing in response to food in the stomach. Moreover, infusion of ghrelin stimulates eating in humans and is the only known hormone secreted from the GI tract to stimulate hunger¹⁵. Weight loss with lifestyle therapy alone has been shown to increase fasting and meal test "active" or acyl-ghrelin concentrations, which correlated with increased hunger on visual analogue scale (VAS) testing¹⁶. Acyl-Ghrelin concentrations were still elevated at one year after weight loss despite weight regain of almost 50%, which suggests that acyl-ghrelin plays an important role in weight regain. Studies investigating ghrelin concentrations in the setting of FF-IGBs have been mixed, demonstrating decreased fasting plasma total ghrelin concentrations¹⁷, no change in fasting or meal test ghrelin concentrations in FF-IGB or control groups^{18, 19}, increased fasting plasma ghrelin compared to a control group at months 1 and 6 with decreased ghrelin in the active arm compared to the control arm after removal²⁰ and increased ghrelin concentrations in a single arm²¹. However, these studies measured

total ghrelin not acyl ghrelin. This limits the reliability of the data especially since no change in ghrelin concentrations were seen in control patients with weight loss in which an increase in acyl- ghrelin is expected. Moreover, all the studies were with FF-IGB and none were in the GF-IGB system.

Balloon type may have an effect on acyl-ghrelin concentrations as GF-IGB tend to float in the fundus and body of the stomach, which may affect the IGB's ability to suppress acyl-ghrelin secretion. In one of the aforementioned studies a post-hoc analysis demonstrated that the small number of patients whose FF-IGBs localized to the fundus had greater suppression of ghrelin¹⁹.

Fasting ghrelin has been evaluated in one study with 12 patients pre and post ESG. Fasting ghrelin concentrations did not increase with weight loss, but meal testing was not performed

²²Therefore, this protocol will determine the effects of 10% TBWL from either GF-IGB system treatment or ESG treatment compared to lifestyle and meal replacement therapy on acyl-ghrelin concentrations, the active form of ghrelin which stimulates hunger, and the sensation of hunger with the VAS. This will allow for the detection of effects that are specific to either procedure and independent of weight loss.

2. Innovation and Knowledge to be Gained: This proposal is innovative for several reasons. It will be the first ever study to evaluate any mechanisms of action of the GF-IGB system approved for use in the US and will add important information to the effect of ESG on gastric emptying as only 4 subjects have had gastric emptying measured pre and post ESG. Second, the study will determine a hormonal response to weight loss by procedures compared with diet through measuring the active form of ghrelin, acyl-ghrelin. Third, no other study investigating mechanisms of action of endoscopic bariatric therapies have compared outcomes with patients achieving the same amount of weight loss through diet alone. Weight loss itself has many effects, and the only way to mitigate the confounding effect of weight loss is to compare changes in these mechanism of action parameters in patients who have the same amount of weight loss, but have not undergone these procedures. Fourth, the study population will come from three clinically administered weight loss programs with different weight loss treatments. Although not a randomized control study, the participant populations in this comparative analysis more closely approximate clinical patient populations. The results from this study will lay the groundwork for future studies into additional gut hormone adaptation, optimization of patient selection to those with the highest likelihood of response to treatment with the GF-IGB system or ESG and studies investigating mechanisms of weight loss maintenance. This information will improve patient outcomes with GF-IGB or ESG treatment by endoscopists.

3. Preliminary Data

The research in this proposal involves using a combination of research techniques including imaging, meal testing, and questionnaires to determine the effects of the GF-IGB system and ESG on gastric emptying, hormonal adaptation to weight loss, and hunger which I have used in two previous studies.

In one study 18 subjects with obesity and nonalcoholic fatty liver disease were randomized in a 1:2 ratio to 16 weeks of: 1) no exercise (BMI 40.0 ± 5.4 kg/m², IHTG $21.3 \pm 10.8\%$) or 2) Exercise at 45%-55% of VO₂ max for 30-60 minutes 5 days/week (BMI 37.1 ± 4.0 kg/m², IHTG $20.4 \pm 6.8\%$). One exercise session per week was monitored at our center and subjects were re-fed calories expended during exercise by providing a liquid formula meal if any change in weight occurred to maintain weight stability. IHTG, measured with magnetic resonance spectroscopy, decreased by $10.3 \pm 4.6\%$ in the exercise group, but did not change in the control group, $p=0.044$. Exercise also decreased plasma alanine transaminase (ALT) concentrations by $12.8 \pm 3.1\%$, $p = 0.04$. Exercise did not affect hepatic lipoprotein secretion rates²³.

In a second study, 11 subjects with obesity were studied before and after a 4-week isocaloric diet high in high-fructose corn-syrup (HFCS). All meals were made in a bionutrition kitchen with 25% of total calories from HFCS. Patients were weighed every 3-4 days at meal pick-up and foods were adjusted to maintain weight. No change in weight (98.2 ± 12.8 kg and 97.8 ± 12.6 , $p=0.336$) or IHTG (2.2% [1.6,3.5] and 3.0% [2.1,6.5], $p=0.424$) measured by MRS occurred during the 4-week trial. Meal testing with a liquid mixed

meal (without HFCS at baseline and with 25% of calories as HFCS at end study testing) revealed trends towards increased fasting plasma uric acid concentrations (5.3 ± 0.8 mg/dl baseline and 5.9 ± 1.4 mg/dl end-study, $p=0.062$) and Uric Acid Area Under the Curve (1188 ± 154 baseline and 1343 ± 335 end-study, $p=0.091$). The high HFCS intervention resulted in a $12.8 \pm 7\%$ increase in plasma total cholesterol concentration, $25.4 \pm 31\%$ increase in plasma triglyceride concentration, and a trend towards an increase in very low-density lipoprotein-triglyceride rate of secretion. No changes were seen in glucose kinetics measured by hyperinsulinemic euglycemic clamp testing (manuscript in preparation).

4. Approach

4.1 Subjects: The study population will consist of 11 patients with a BMI 30-40 kg/m² and age 22-65 years old who are weight stable (defined as <5% weight change in the last 3 months) and initiating clinical treatment with the GF-IGB system, 11 patients with a BMI 30-40 kg/m² and age 22-65 years old who are weight stable (defined as <5% weight change in the last 3 months) and initiating clinical treatment with ESG, and 11 patients with a BMI 30-40 kg/m² and age 22-65 who are weight stable and initiating clinical treatment with a medically supervised MRP (My New Weigh; University of Colorado, Anschutz Health and Wellness Center). After undergoing any required laboratory testing or imaging for the patient's self-chosen treatments, patient will present for screening. The screening visit will consist of a history and physical examination, the Patient Health Questionnaire- 9 (PHQ-9)²⁴, and the Questionnaire on Eating and Weight Patterns – 5²⁵ (Appendix A). Patients with a history of liver disease, uncontrolled thyroid disease, anemia, diabetes, eating disorder, uncontrolled depression defined as a score ≥ 10 PHQ-9, on weight loss medications in the last 3 months, history of gastroparesis, bariatric surgery, or history to allergy or intolerance to any component of the meal used in the gastric emptying study or mixed meal test will be excluded. Women who are pregnant or lactating, prisoners, non-English speakers, and decisionally challenged adults will also be excluded. We anticipate consenting 25 patients in each arm to achieve the required number of patients completing all study testing in each arm for achieve adequate statistical power (See 5.2 Power Calculation). We will attempt to match enrollment based on BMI in categories of BMI 30-34.9 kg/m² and 35-40 kg/m².

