5.1 Data analysis. The primary analysis will be a group by study-time repeated (baseline-end study) measures analysis of variance which will include an evaluation of statistical contrasts that compare between group differences in changes from baseline to end. Analyses will be performed on the following variables: percent of gastric retention at 2 hours, fasting and Area Under the Curve (AUC) for acyl ghrelin, insulin, glucose, and VAS-hunger. A Student's t-test for paired samples will also be performed on each variable from baseline to end-study testing. All data will be analyzed using SPSS (IBM, Armonk, NY)

5.2 Power calculation. The primary endpoints used for the power calculation in this study are change in gastric emptying at 2 hours, acyl-ghrelin concentrations, and visual analog scale. In assessing statistical power, we will use statistical contrasts of change from baseline between the groups, assuming 11 patients in each group. Based on previous work, a conservative estimate of standard deviation of the change is assumed to be roughly 80% of the amount of change for fasting acyl-ghrelin and VAS Hunger (16) and 60% for percent gastric retention at 2 hours ¹¹. All tests are two-sided and performed at the 0.05 level of significance. GPower 3.1 (Universitat Duesseldorf, Germany) was used for power calculations. The impact of these assumptions is as follows (Table 1):

Table 1. Power Calculations

Variable	Baseline	Response to Weight Loss			Between Group (compared with MRP)	
		MRP	GF-IGB	ESG	GF-IGB	ESG
% Retention at 2 hours	25±14.5%	0	+12.5 (50%)	+12.5 (50%)	96%	96%
Acyl Ghrelin pg/ml	125±100	+50 (40%)	+10 (8%)	+10 (8%)	86%	86%
Visual Analog Scale	32±25	+11 (40%)	0	0	80%	80%

6.0. Study timeline.

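### The plan predicts no glucose or insulin difference between groups and no hunger change in the device arms, but its difference tests can only contradict these predictions, not establish them

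*Combined protocol and SAP*

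**What the plan says.** Two clauses in the Specific Aims predict the absence of an effect. Hypothesis 2 ends "but there will be no difference in glucose and insulin concentrations", a comparison of the device arms with MRP. Hypothesis 3 says that hunger "will not change from baseline after weight loss with GF-IGB or ESG treatment", a statement about change within each device arm. The other half of Hypothesis 3, that "hunger will increase before and during a MMT after weight loss with MRP", predicts an effect.

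Section 5.1 gives every variable the same two analyses. One is a repeated-measures analysis of variance with "statistical contrasts that compare between group differences in changes from baseline to end"; the other is a "t-test for paired samples will also be performed on each variable from baseline to end-study testing". For acyl-ghrelin, insulin, glucose and VAS hunger, both the fasting value and the AUC are analysed.

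Section 5.2 adds: "All tests are two-sided and performed at the 0.05 level of significance". The endpoints used for power "are change in gastric emptying at 2 hours, acyl-ghrelin concentrations, and visual analog scale"; glucose and insulin are not among them. Neither section gives an equivalence margin, an interval criterion or any other rule for concluding that there is no difference or no change.

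**The concern.** A two-sided difference test can reject a prediction of no effect. When it does not reject, it has shown only that the data are compatible with zero, and with 11 patients per arm they will also be compatible with a range of non-zero effects. The plan offers no other route to the two null conclusions.

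This matters because of what the trial is for. The Aims say that it should shed light on effects on glucose control that do not depend on weight loss, and that it should prepare the ground for later studies. A non-significant glucose or insulin contrast, or a non-significant paired test of hunger in a device arm, could be taken as support for the hypothesis when the trial could not have seen an effect of moderate size.

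**Working it through.** **Inputs.** From 5.2: 11 patients per group, two-sided 0.05, and an SD of change "assumed to be roughly 80% of the amount of change for fasting acyl-ghrelin and VAS Hunger". From Table 1: a VAS rise of 11 with MRP and 0 in the device arms, with baseline VAS 32±25. The documents give no SD for glucose or insulin, so those results are in units of the SD of change.

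**The plan's own VAS figure.** SD of change = 0.80 × 11 = 8.8, so d = 11/8.8 = 1.25. With noncentrality d × √(11/2) = 2.93 and 20 degrees of freedom, power is 79.6%; Table 1 says 80%. The device-versus-MRP contrast for hunger is powered as stated.

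**Glucose and insulin, one contrast, 11 versus 11** (two-sample noncentral t):
- Chance of p>0.05 is 79.9% at a true difference of 0.5 SD and 56.9% at 0.8 SD.
- 95% interval half-width = t(0.975; 20) × √(2/11) = 2.086 × 0.426 = 0.89 SD. With error pooled over three arms (30 degrees of freedom) it is 0.87 SD.
- Two one-sided tests at 0.05, with a true difference of zero, have power 6% at a margin of 0.70 SD and 47% at 1.0 SD. They reach 80% only at about 1.29 SD.

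**Glucose and insulin, the whole clause.** Fasting and AUC, two analytes and two device arms make 2 × 2 × 2 = 8 contrasts. The documents give no correlations, so the four measures were simulated at assumed correlations of 0, 0.5 and 0.8, with the same true difference in all eight contrasts. The chance that all eight are non-significant is:

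| True difference in every contrast | Correlation 0 | 0.5 | 0.8 |
|---|---|---|---|
| 0.5 SD | 22% | 37% | 49% |
| 0.8 SD | 3% | 12% | 21% |

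**Hunger within one device arm, n = 11.** The 80% rule gives no usable SD here, because 80% of an assumed zero change is zero. If MRP's 8.8 is borrowed, the 95% interval half-width is t(0.975; 10) × 8.8/√11 = 2.228 × 2.653 = 5.9 points, and a true rise of 5.5 (half of 11) is non-significant 53% of the time.

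That 8.8 may be low. If ±25 in Table 1 is an SD and is similar at end of study, SD of change = 25 × √(2(1 − r)), where r is the baseline-to-end correlation. Setting this to 8.8 requires r = 1 − 8.8²/(2 × 25²) = 0.94. The chance that the upper 95% limit falls below +11 when the true change is zero is the probability that a noncentral t on 10 degrees of freedom, with noncentrality 11√11/SD, exceeds 2.228:

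| SD of change | Where it comes from | Chance of excluding +11 |
|---|---|---|
| 8.8 | borrowed from MRP (r = 0.94) | 96% |
| 13.2 | 1.5 × 8.8 | 70% |
| 15.8 | r = 0.8 | 55% |
| 17.6 | 2 × 8.8 | 47% |
| 25 | r = 0.5 | 26% |

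**The case against.** The strongest reply is that these are scientific predictions in a pilot, not decision rules. A reader might infer that the plan will report p>0.05 as no effect. The documents do not say so; they set no confirmation rule for any hypothesis, and a difference test is a reasonable way to look for an effect on glucose control. That stands and limits the weight of the point. The gap is that nothing is planned that could support the two clauses.

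Second, hunger is largely handled by the device-versus-MRP contrast, which is planned and powered. That also stands. It would be wrong to infer that Hypothesis 3 as a whole cannot be tested: the predicted MRP rise suits the paired t-test, and the contrast addresses whether the device arms differ from MRP. Only the claim of no change within a device arm is left without support.

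Third, one could read the 80% and 57% as the chance that Hypothesis 2 is falsely confirmed. They are per-contrast figures. If differences are broad, the chance that all eight contrasts are missed is lower, as the simulation shows; if only one contrast truly differs, the per-contrast figure applies to it. The interval width is the same either way.

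Fourth, because the paired test has 96% power against +11 at an SD of 8.8, a reader might infer that the trial can at least exclude an MRP-sized rise in hunger. The documents do not support that as a general statement. It rests on an SD borrowed from another arm. The benchmark is also uncertain: Table 1 labels +11 as 40%, but 11/32 is 34% and 40% of 32 is 12.8. No AUC equivalent is stated, although the hypothesis covers hunger during the meal as well as before it.

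Finally, the omission of glucose and insulin from the power calculation is normal in a pilot and is not a separate defect.

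**Conclusion.** The point holds for two clauses only: no between-group difference in glucose and insulin, and no change in hunger within the device arms. The planned tests can refute these clauses but cannot support them. A single non-significant glucose or insulin contrast with an estimate near zero would leave differences of up to about 0.9 SD unexcluded; without an SD this cannot be put in clinical units. For hunger, what 11 patients can exclude is unknown at the planning stage. The range of 96% down to 26% for a rise of 11 assumes zero true change, normally distributed changes and, for SDs of 15.8 and 25, that Table 1's ±25 is an SD that holds at both visits.

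The weight is modest, CONSIDER. The contrasts for gastric retention, acyl-ghrelin and hunger against MRP are unaffected. What changes is which conclusions the trial may draw from non-significant results.

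**What to change.** 1. In Hypothesis 3, keep the MRP prediction and its paired t-test. Replace the device-arm clause with: *the change in hunger from baseline will be smaller with GF-IGB or ESG than with MRP*. Test it by the between-group contrast already in 5.1 and report its 95% confidence interval. Report each device arm's own change, for fasting and AUC hunger, with a 95% interval, without promising that an MRP-sized rise can be excluded.
2. Restate the glucose and insulin clause of Hypothesis 2 as estimation: *between-group differences in change in fasting and AUC glucose and insulin will be estimated with 95% confidence intervals (exploratory)*.
3. Add to 5.1: *p>0.05 will not be interpreted as no difference or no change*.

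A formal equivalence test is not proposed. For glucose and insulin only very wide margins are within reach of 11 per arm, and for hunger its power depends on the unknown SD.

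The cost is a rewording of two clauses in the Aims and short additions to 5.1, with no new patients, no new data and no planned test removed. The trial gives up the claims of no difference and no change, which its tests could not support.
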